## 4. Name and address of the referral (support) organization

N/A

## 5. Drugs and Devices for the research

**Aerobika (Trudell Medical International, London, ON)**

## 6. Background of the research

Bronchiectasis is a chronic lung disease characterized by permanent dilation of the bronchus, often accompanied by chronic respiratory symptoms and recurrent lung infections and inflammation. It is one of the most common chronic respiratory diseases worldwide, and its prevalence has been steadily increasing in recent years. Patients with bronchiectasis experience a significant disease burden, with lower quality of life and more frequent access to health care compared to the general population.

Our findings showed that the prevalence of bronchiectasis in Korea is higher than that in the United States and Europe (Germany, United Kingdom, etc.), and given the high incidence of tuberculosis in Korea, the disease burden of bronchiectasis, one of the major complications of

tuberculosis, is significant for both patients and the country. In particular, the disease burden of bronchiectasis is strongly associated with acute exacerbations.

Acute exacerbations of bronchiectasis can be caused by a variety of factors, including fine dust, bacteria, and non-tuberculous antibacterial infections, and can result in worsening sputum and dyspnea symptoms, requiring hospitalization or, in severe cases, intensive care unit treatment. Most patients with bronchiectasis will experience at least one acute exacerbation in their lifetime, and the main goals of treatment are to reduce acute exacerbations and infections, reduce airway inflammation, and facilitate sputum clearance to improve the patient's quality of life.

The British Thoracic Society guideline for bronchiectasis in adults, published in the journal Thorax in 2019, recommends that patients with bronchiectasis should be offered individualized airway management. Airway management techniques include using the Active Cycle of Breathing Technique and Oscillating PEP (OPEP), which are known to be effective in clearing sputum and have a positive impact on improving patients' quality of life. When applied to bronchiectasis patients with frequent acute exacerbations, OPEP has been shown to improve symptoms and reduce acute exacerbations. However, previous study was a pilot study, which have been limited by the small number of patients enrolled and the lack of a control group.

## **7. Research Objective**

To evaluate the effectiveness of active cycle of breathing techniques alone versus active cycle of breathing techniques therapy plus an Oscillating Positive Expiratory Pressure (OPEP) device in reducing the occurrence of acute exacerbations and improving symptoms in patients with bronchiectasis who have experienced 3 or more acute exacerbations within 1 year.

## **8. Risk and Benefit**

: For patients who experience frequent acute exacerbations more than three times per year, the use of OPEP in addition to active cycle of breathing techniques may improve quality of life and reduce acute exacerbations.

On the other hand, rare side effects of OPEP use include hemoptysis and pneumothorax, but these are very rare (<0.1% in existing reports) and the risk can be reduced by selecting patients with fewer side effects.

## **9. Selection and Exclusion Criteria for Subjects**

### **Total Subject: 100 patients**

control group : 50 patients with bronchiectasis using active cycle of breathing techniques  
experimental group : 50 patients with bronchiectasis using ACT and OPEP simultaneously

The control and test groups will be randomly assigned by the research nurse, and neither the physician nor the patient will be aware of this.

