**Selection criteria:**

- 18 years of age or older
- Patients diagnosed with bronchiectasis involving one or more lobes on chest computed tomography (CT)
- Patients experiencing frequent exacerbations (with 3 or more exacerbations) within 1 year
- Patients able and willing to use the Aerobika device (OPEP)

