**Exclusion criteria :**

- diagnosis of bronchiectasis due to cystic fibrosis
- traction bronchiectasis due to interstitial lung disease (ILD)
- pregnant patients
- patients with a history of OPEP device use
- patients who cannot tolerate increased breathing work
- hemodynamic instability (e.g., unstable blood pressure)
- patients with a past or current history of hemoptysis (pulmonary bleeding) and untreated pneumothorax

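### The protocol says, with no time limit, that patient and physician will be unaware of the assignment, which cannot hold for patients given the OPEP device

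*Protocol*

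**What the plan says.** Section 9 (Selection and Exclusion Criteria for Subjects) sets 50 patients per arm, has the research nurse randomise them, and states that "neither the physician nor the patient will be aware of this". It describes the test arm as "experimental group : 50 patients with bronchiectasis using ACT and OPEP simultaneously". The control arm uses the breathing techniques only.

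Section 7 (Research Objective) gives the same comparison: "active cycle of breathing techniques alone versus active cycle of breathing techniques therapy plus an Oscillating Positive Expiratory Pressure (OPEP) device". Section 5 lists one device, the Aerobika. The selection criteria require every participant to be able and willing to use it, and the exclusion criteria rule out "patients with a history of OPEP device use". Section 11 has the study explained to each patient in person before consent. Section 19 provides for teaching patients how to begin and to blow at a lower pressure.

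**The concern.** A reader who takes the sentence in Section 9 at face value will understand that patients and physicians stay unaware of the arm throughout the trial. The rest of the protocol describes a visible device in one arm and nothing comparable in the other.

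What is at stake is how the symptom and quality-of-life results may be interpreted. Section 8 states the expected benefit: "the use of OPEP in addition to active cycle of breathing techniques may improve quality of life and reduce acute exacerbations". If patients are told this, expectation would tend to favour the device arm in any score that they report themselves. A difference in mMRC, BHQ or CAT could then be presented as a blinded device effect although the patients knew their treatment.

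**Working it through.** The protocol gives no figure to reproduce here. The check sets its statements side by side.

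1. **Scope of the statement.** Section 9 covers both the physician and the patient. It names no stage, such as up to randomisation, and no point at which unawareness ends.
2. **What differs between arms.** By Sections 7 and 9, the device is given to the experimental arm only.
3. **Whether the patient can tell.** The device is the only one listed in Section 5. The teaching in Section 19 reads as teaching for the device, because Section 8 attributes the same two rare side effects to OPEP use. Earlier users are excluded, so a newly issued OPEP device identifies the arm.
4. **Whether anything masks the difference.** No section shown describes a sham, a masked comparator or a time limit on the unawareness.
5. **Device arm.** A patient who has consented to this study and been issued and taught the device knows the assignment. That is 50 of 100 patients, or 50%.
6. **Control arm.** These patients had to be willing to use the Aerobika, had the study explained in person, and receive no device. They can probably infer their arm. This is an inference, because Section 11 does not list what the explanation contains.
7. **Physician.** A physician who neither issues nor discusses the device could remain unaware. No section shown says how this would be arranged. That is silence, not a contradiction.

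**Outcomes exposed**

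- Section 16 names four measures for symptoms and quality of life: mMRC, BHQ, CAT and PFT. The first three are patient-reported, so the share is 3/4.
- Section 14 collects those three at every visit, with follow-up at 1, 3, 6, 9 and 12 months. Before any missed visit or dropout, that gives 5 visits × 3 questionnaires × 100 patients = 1,500 completions after assignment, of which 5 × 3 × 50 = 750 are in the device arm. These counts show exposure to knowledge of the arm. They do not measure error.
- Section 16 also counts acute exacerbations. The nearest working definition is in Section 14: three or more major symptoms worse for at least 48 hours, with a change in treatment. It is printed there as a definition of adverse events, so reading it as the exacerbation definition is an inference. The background in Section 6 agrees, saying that exacerbations "can result in worsening sputum and dyspnea symptoms". On that reading, exacerbations are exposed so far as they rest on symptom reports and treatment decisions.

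**The case against.** The strongest reply is that the sentence was never a claim of blinding. Its nearest antecedent is the nurse's act of assignment, it stands in the section on subject selection, and the protocol as shown nowhere calls the trial blinded, double-blind or masked. Read as allocation concealment, it agrees with every other section. A reader can also see that a device is being compared with no device, and no section shown plans to report blinded outcomes.

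Much of this stands. Concealment is a plausible reading, and it is the reason for treating this as a wording fault and not a design failure. It does not rescue the sentence as written, which sets no limit. If concealment was meant, the sentence needs to say so. If a sham was meant, it needs to be described. It has to change either way.

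Three stronger readings are tempting and are not supported:

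- **That physician blinding is impossible.** It could be arranged. The protocol as shown does not say how.
- **That the device-versus-no-device comparison is itself a fault, or that outcome assessors must be masked.** The protocol says nothing wrong on assessor masking, and its silence there is not an error.
- **That a particular amount of bias or inflated error rate follows.** The documents give no effect size, standard deviation or significance level. Any such figure would rest on assumed reporting shifts, would apply equally to a trial openly described as unblinded, and would not be reduced by rewording.

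**Conclusion.** The point holds as a contradiction in wording. As written, the statement cannot be true for the 50 device-arm patients after the device is issued. It is probably untrue in practice for control patients, and it is unsupported, though possible, for physicians. It affects what may be concluded from three of the four symptom and quality-of-life measures and, to a lesser and undefined extent, from exacerbations.

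This rests on two assumptions: that no sham is described in the parts of the protocol that are not shown, and that the teaching in Section 19 concerns the OPEP device. A reader might infer that the sponsor has claimed a double-blind trial. The documents do not support that, because the sentence may have meant concealment only. The sentence should be fixed, but the point does not call the design of the trial into question.

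**What to change.** Reword the sentence in Section 9 to say who is unaware, of what, and until when, and reconcile it with Section 7, the selection criteria and Section 19. If no sham is intended, for example:

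*The assignment is concealed from patient and physician until eligibility, consent and baseline measurements are complete; patients are not blinded after the OPEP device is issued.*

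This example fixes an order that Section 14 leaves open, since that section places randomisation at the baseline visit without saying whether the measurements come first. The sponsor should confirm that the order is workable. If a sham is intended, describe it. If the physician is meant to stay unaware during follow-up, say how.

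Report mMRC, BHQ and CAT as unblinded patient-reported outcomes. Note that exacerbations are exposed so far as they depend on symptom reports and treatment changes.

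The cost is one or two sentences of protocol text. The trial can then no longer be described as patient-blinded. The change corrects the description only, and any reporting bias from patients knowing their arm remains.

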**Selection criteria:**

- 18 years of age or older
- Patients diagnosed with bronchiectasis involving one or more lobes on chest computed tomography (CT)
- Patients experiencing frequent exacerbations (with 3 or more exacerbations) within 1 year
- Patients able and willing to use the Aerobika device (OPEP)

**Exclusion criteria :**

- diagnosis of bronchiectasis due to cystic fibrosis
- traction bronchiectasis due to interstitial lung disease (ILD)
- pregnant patients
- patients with a history of OPEP device use
- patients who cannot tolerate increased breathing work
- hemodynamic instability (e.g., unstable blood pressure)
- patients with a past or current history of hemoptysis (pulmonary bleeding) and untreated pneumothorax

**10. Basis for calculating the number of target group**

: Based on a pilot study previously conducted at our institution to determine the number of eligible participants

**11. Methods of recruiting subjects and consent procedures**

: Patients attending the outpatient department of respiratory internal medicine for bronchiectasis at Chungbuk National University Hospital who have experienced 3 or more acute exacerbations within 1 year will be selected and informed consent will be obtained after explaining the study in person.

**12. Safeguards for recruiting vulnerable populations**

- Patients who are classified as vulnerable research subjects will not be solicited to participate in the study, and only those who voluntarily agree to participate in the study will be included.
- Only for individuals who have read and understood the informed consent document and have voluntarily signed an informed consent form (guardian consent if patient is unable to consent)
- There will be no impact regarding the relative threat to the patient's care from participation or non-participation in the study
- Ensure that consent is obtained from both the subject and their legal representative.

### **13. Screening test methods**

Not necessary because it targets patients already diagnosed with bronchiectasis

### **15. Standard treatment of target disease**

There is currently no established standard treatment.

### **16. Validity assessment methods**

Improvement of patient symptoms and quality of life through mMRC, BHQ, CAT score, and PFT  
Measuring the frequency of acute exacerbations during the study period

### **17. Statistical analysis methods**

Continuous variables were analyzed using t-test or Mann-Whitney U test. Categorical variables were compared using Pearson Chi-square test, Fisher's Exact test.

**18. Clinical study drop-out criteria**

N/A

**19. Predicted side effects and precautions for use**

Rare cases of hemoptysis and pneumothorax have been reported, and patient education will include instructions on how to start and blow with lower pressure

**20. Criteria, methodology, and reporting of safety, including adverse events**

N/A

**21. Estimated study duration**

2 years from IRB approval date

**22. Protecting privacy and confidentiality of research data**

: The information collected is from patient's medical record, or information such as the type, date, procedures and results of various tests. This information may include information from the subject's medical record and information created or collected during the clinical study. However, all information collected will be processed with code numbers and initials so that it is not recognizable as information about the subject, and relevant documents will be stored in a locked file cabinet.

No personal information will be collected

**23. Managing, storing, and disposing of human remains when collected****Human derived materials Research Consent Process**

Because we will be collecting human derived materials, respiratory samples and blood directly from human subjects, we will obtain written informed consent and human derived materials research consent from those who provide human derived materials.

It is provided in accordance with 「Personal Information Protection Act, Article 15 - Collection and Use of Personal Information and Bioethics-related Laws」 including the purpose of collecting and using personal information, items collected, period of collection and use, provision of information to third parties, and refusal of consent to collection and use.

Clarify that consent is given on a voluntary basis, without coercion, and that there will be no adverse consequences to the subject if the subject refuses to participate in the research or discontinues participation during the research.

**Method to use and dispose of human derived materials**

Human derived materials will be analyzed as anonymous coded data without personal identifiers and will be stored for 3 years after the end of the study before being disposed. On the other hand, specific information identified during the analysis will be shared with co-investigator and used for reporting results and papers without recording personal information.

After testing, the remaining samples will be stored in the refrigerator in their original state considering the possibility of retesting, and after all test results and analysis are completed, they will be classified and disposed of according to Article 4 (Kinds of Medical Waste).

**24. A plan for statistical analysis of the study, including a plan for interim analyses and scope for early termination of the study if necessary.**

: N/A

**25. Continuous Safety Monitoring Plan and Material Safety Monitoring Plan**

: The results of the data safety monitoring exercise should be reported to the appropriate IRB at the time of the interim report or end/outcome report.

**26. Methods to ensure the research is ethical**

We will conduct research in accordance with approved protocols and investigator compliance, and will ensure compliance with the Declaration of Helsinki and ICH-GCP standards and all applicable regulations.

The research will be conducted in accordance with the approved research protocol and researcher compliance, and all data from research subjects will be anonymized, kept strictly confidential, password protected, in separate files, and not identifiable through the research data.

**27. Data storage**

Data obtained from this study will be kept for up to 10 years after the end of the study and then destroyed immediately.

**28. Research plan (timeline)**

Duration (month)	1	2	3	4	5	6	7	8	9	10	11	12
IRB review												
Patient Registration												

Patient f/u											
debrief											

